9.1.4 Expectedness

Assessment of expectedness will be made by the Investigator against the current version of the Investigator Brochure. If updated versions of the Investigator's Brochure are released during the course of the trial then assessment of expectedness will be made against the updated version.

9.1.5 Suspected, unexpected, serious, adverse reactions (SUSAR)

A SUSAR is a suspected, unexpected, serious adverse reaction. All AEs and SAEs will be assessed for seriousness, causality and expectedness. An SAE will be considered to be a

SUSAR if it is possibly, probably or definitely related to CTC3833 and has not previously been reported. The Investigator and study team will rapidly report all SUSARs to the RM-CTU within 24 hours of becoming aware of the event. The RM-CTU will ensure that the Sponsor, the MHRA and main REC are notified within the timelines specified in legislation (SI 2004/1031 as amended).

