6.4 Definition of dose-limiting toxicity

The dose-limiting toxicity (DLT) is defined using the National Cancer Institute's (NCI) Common Terminology Criteria for Adverse Events (CTCAE) version 4.03 (Appendix 4). DLTs identified in Cycle 1 of treatment will inform the decision to dose escalate through the increasing dose levels. Significant toxicities and DLTs in later cycles will be considered throughout the treatment period and in determining the recommended Phase 2 dose.

A DLT is defined as a probably or highly probably drug related toxicity as detailed in Table 8.

Table 8: Dose-limiting toxicity definitions and criteria

Toxicity	Criteria
Any toxicity causing a decrease in treatment dose intensity	Inability to deliver > 75% of the planned dose intensity in a cycle due to CCT3833-related toxicity
Haematology	
 • Grade 4 neutropenia for > 1 week • Grade 4 thrombocytopenia or grade 3 thrombocytopenia with bleeding • Febrile neutropenia • Grade 4 anaemia (unless a specific cause of blood loss is identified)
Cardiovascular	
 • Any grade 3 or above • Hypertension (grade 3 or above) lasting more than 2 weeks despite optimal treatment
Skin	Any grade 3 or above, persisting for > 7 days despite optimal treatment
Metabolic	Grade 3 or above hyperglycaemia (measured in the fasted state)
Any other drug related G3/4 toxicity except:	
 • Alopecia • Nausea that is sub optimally managed • Vomiting that is sub optimally managed • Diarrhoea that is sub optimally managed • Constipation that is sub optimally managed
Any other toxicity that is considered dose-limiting in the view of the Investigator	

Baseline laboratory values are those reported before the first dose of CCT3833.

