- h) Laboratory tests will be performed alongside each clinical visit; clinical laboratory assessments should therefore be performed on Days 1, 8, 15, 22 during Cycles 1 and 2. The frequency can be reduced to Days 1 and 15 from Cycle 3 onwards at the discretion of the Investigator, and reduced again to once a month (pre-dose on Day 1) from Cycle 5 onwards. In the event of a grade 4 neutropenia or grade 4 thrombocytopenia, a full blood count must be performed at least on Day 5 after the onset of the event to determine if a DLT has occurred. Continue close monitoring until resolution to grade 3 or less. Non fasting glucose, and LDH are required for biochemistry. If non fasting glucose >7.8 mmol/l, repeat as a fasting glucose. If this too demonstrates grade 3 hyperglycaemia, a formal glucose tolerance test should be undertaken, and appropriate management of hyperglycaemia initiated.
- i) An echocardiogram will be performed pre-study and at the start of Cycle 2 (± 3 days). It will then only be repeated as clinically indicated.
- j) 4 mL blood samples for PK assessment will be taken for all patients between Day-3 and Day-7, and on C2D1 at twelve time points: pre-dose on the day of dosing, 15 min (± 5 min), 30 min (± 5 min), 1 h (± 5 min), 1.5 h (± 10 min), 2 h (± 10 min), 3 h (± 10 min), 4 h (± 15 min), 6 h (± 15 min), 8 h (± 15 min), 12 h (± 60 min), 24 h (± 120 min) and 48 h (± 120 min; Day -7 to Day -3 admission only) post-dose. The same C2D1 sampling schedule will be used for patients that are dose escalated on C2D1 of the increased dose
- k) Monthly follow-up only required for those AEs and SAEs considered drug-related (highly probably, probably, or possible) that are present at time patient ends the study. Monthly follow-up to continue until resolution to baseline, stabilisation or patient starts another anticancer treatment.

Table 15: Schedule of events- Dose expansion stage

Observation/Investigation	Pre-study		Standard evaluations for each cycle of CCT3833; 1 cycle = 28 days				Off study	Follow up (for AE until resolution)
	Between Day -28 and Cycle 1	Between Day -7 and Cycle 1	Cycle 1, Day 1 (± 1day)	Day 15 (± 1day)	Cycle 2, Day 1 (± 1day)	Monthly thereafter if no DLT observed (± 1day)	(± 3 days)	Monthly
Written informed consent	x							
Demographics and height	x							
Medical history	x							
Availability of historical tumour biopsy	x							
Radiological assessment ^A	x		At end of every 2 cycles				x	

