9.1.2 Serious adverse events

A serious adverse event (SAE) is any AE, regardless of dose, causality or expectedness, that:

- results in death.
- is life-threatening.
- requires in-patient hospitalisation or prolongs existing in-patient hospitalisation (some hospitalisations are exempt from SAE reporting – see section 9.2.1).
- results in persistent or significant incapacity or disability.
- is a congenital anomaly or birth defect.
- is any other medically important event.

For screening failures, SAEs will be reported to the RM-CTU from the date of consent until the date the patient is confirmed as ineligible. For eligible patients, SAE and AE collection and monitoring commences from the time the patient gives their written consent to participate in the trial and continues for 28 days after the last administration of the IMP.

Follow-up of AEs with a causality of possibly, probably or highly probably related to the IMP will continue until the events resolve, stabilise or the patient starts another anti-cancer therapy.

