9.1.3 Determining adverse event causality

The relationship of an AE to the IMP is determined as follows:

Highly probable

- Starts within a time related to the IMP administration and
- No obvious alternative medical explanation.

Probable

- Starts within a time related to the IMP administration and
- Cannot be reasonably explained by known characteristics of the patient's clinical state.

Possible

- Starts within a time related to the IMP administration and
- A causal relationship between the IMP and the AE is at least a reasonable possibility.

Unlikely

- The time association or the patient's clinical state is such that the trial drug is not likely to have had an association with the observed effect.

Not related

- The AE is definitely not associated with the IMP administration.

Note: Drug-related refers to events assessed as possible, probable, highly probable or definitely.

The Investigator must endeavour to obtain sufficient information to determine the causality of the AE (i.e. IMP, other illness, progressive malignancy etc) and must provide his/her opinion of the causal relationship between each AE and IMP. This may require instituting supplementary investigations of significant AEs based on their clinical judgement of the likely causative factors and/or include seeking a further opinion from a specialist in the field of the AE.

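### The SUSAR sentence in 9.1.5 does not match the causality scale in 9.1.3, the Brochure standard in 9.1.4 or its own opening lines

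*Combined protocol and SAP*

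**What the plan says.** Section 9.1.3 sets out five causality grades: highly probable, probable, possible, unlikely and not related. The top grade requires a plausible time relation to dosing and "No obvious alternative medical explanation". A note below the scale adds that "Drug-related refers to events assessed as possible, probable, highly probable or definitely", so a further term appears there without a definition.

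Section 9.1.4 fixes the standard for expectedness: "Assessment of expectedness will be made by the Investigator against the current version of the Investigator Brochure". If the Brochure is updated during the trial, the updated version applies.

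Section 9.1.5 begins by spelling out SUSAR as suspected, unexpected and serious, and says that events are to be assessed for seriousness, causality and expectedness. Its next sentence gives the working rule: an SAE is a SUSAR if it is "possibly, probably or definitely related to CTC3833 and has not previously been reported". Sites then report SUSARs to RM-CTU within 24 hours, and RM-CTU sees that the Sponsor, MHRA and main REC are notified within the statutory timelines.

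Section 9.2 separately requires every SAE, whatever its causality, to reach RM-CTU within 24 hours.

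**The concern.** The sentence that decides SUSAR status differs from the protocol's own definitions in two ways. Its causality terms are not those on the scale that investigators use, and its second condition turns on earlier reporting instead of the Brochure.

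The classification matters because 9.1.5 ties notification of the Sponsor, MHRA and main REC to it. This is a first-in-man trial, and 1.2.1 states that there is no clinical experience with the product yet. Serious reactions not listed in the Brochure are therefore a realistic prospect, and both a clearly drug-caused case and a recurrence are informative to those bodies. With two tests in adjacent sections, two careful readers could classify the same event differently.

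**Working it through.** No arithmetic applies, and the plan gives no figure to reproduce. The check compares the definitions and then applies each to the same events.

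**Causality terms**

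- 9.1.3, defined drug-related grades: possible, probable, highly probable.
- 9.1.3, note: the same three plus *definitely*, listed as a separate term.
- 9.1.5, SUSAR sentence: possibly, probably, definitely.
- 6.4: "A DLT is defined as a probably or highly probably drug related toxicity as detailed in Table 8".
- 9.1.2: "Follow-up of AEs with a causality of possibly, probably or highly probably related to the IMP will continue".
- Footnotes to the schedules of events (Tables 14 and 15): "considered drug-related (highly probably, probably, or possible".

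*Highly probable* is thus the top grade wherever the DLT and follow-up rules use the scale. As a grade of relatedness, *definitely* occurs only in the 9.1.3 note and the SUSAR sentence. One of the three defined drug-related grades is not named in the SUSAR sentence.

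**Expectedness**

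Section 9.1.4 asks whether the reaction is in the current Brochure. The SUSAR sentence asks whether something has been reported before, without saying what or to whom. Two readings are considered: the *type* of reaction has not been reported, or this *individual episode* has not been reported.

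**Both rules applied to the same SAEs**

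| SAE | 9.1.3 with 9.1.4 | SUSAR sentence, read literally |
|---|---|---|
| Probable, not in Brochure, first case | SUSAR | SUSAR |
| Highly probable, not in Brochure, first case | SUSAR | Not a SUSAR: grade not named |
| Probable, still not in Brochure, second patient | SUSAR | Type reading: not a SUSAR. Episode reading: SUSAR |
| Probable, in Brochure, not yet reported | Not a SUSAR | SUSAR |

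The rules agree on the first row. The second differs because of the causality wording alone. The third differs only on the type reading. The fourth differs on both readings, in the direction of over-inclusion. On the episode reading the repeat case is no longer lost, but the sentence then contains no test of expectedness, because any new related SAE would satisfy it.

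**The case against.** The strongest reply is that 9.1.5 should be read as a whole. It opens with the word unexpected, requires expectedness to be assessed, and follows directly after the section that names the Brochure as the standard. A reader might infer from the operative sentence that the expectedness test has been replaced. The documents do not support that: the section states the right test and then contradicts it. This part of the reply stands and limits the point to an inconsistency.

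Second, *definitely* is plausibly a mislabel for the top grade. The 9.1.3 note counts highly probable events as drug-related, and in ordinary language such an event is at least probably related. A reader might infer that the protocol means to exclude the most clearly drug-caused events; nothing suggests that intention. Even so, no text equates the two terms, and the note lists them side by side as different ones.

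Third, a reader might infer that every case of an unlisted reaction after the first would be lost. That holds only on the type reading. In 9.2, the idea of a previously reported SAE attaches to an individual event, and each episode has its own form, which favours the episode reading. It also assumes that the reaction stays out of the Brochure, although 9.1.4 provides for updates. No count of missed cases should be attached to this.

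Fourth, safeguards remain. A reader might infer that expedited reporting as such fails, but RM-CTU receives every SAE within 24 hours (9.2) and is responsible for pharmacovigilance (11.3.1). The SRC reviews all AEs before escalation (6.8) and, with the investigators, reviews safety data regularly (9.3). A recurring serious reaction would therefore still be visible inside the trial. These safeguards do not correct the classification on which notification of the MHRA and main REC depends. The reference to legislation in 9.1.5 concerns the timelines for notification and does not restate the definition.

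**Conclusion.** The point holds as an internal inconsistency that should be corrected. The SUSAR sentence is wrong as written: it leaves one of three defined drug-related grades unnamed, relies on an undefined one, and sets a condition that disagrees with 9.1.4. Its reach is onward SUSAR notification only.

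The possible under-notification of highly probable events rests on a literal reading of the causality terms. That of repeat cases rests further on taking the reporting test to mean the type of reaction, and on the Brochure not yet listing it. The possible over-inclusion of Brochure-listed reactions holds on both readings considered. The documents give no basis for a rate of misclassified events, and they do not show that any event has been or would be missed in practice. The DLT rules, escalation, endpoints, sample size and analysis are unaffected.

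**What to change.** Reword the operative sentence of 9.1.5 along these lines: *an SAE is a SUSAR if its causality is graded possible, probable or highly probable (section 9.1.3) and it is unexpected when judged against the current Investigator Brochure (section 9.1.4).* Delete the condition about earlier reporting. In the 9.1.3 note, delete *definitely* or give it a definition; if it is kept as a grade, carry it through every rule that uses the scale. In the same edit, correct the product code in 9.1.5, where two letters are transposed relative to CCT3833.

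The cost is one sentence and one note, using definitions already in the protocol, plus the amendment route in 11.1. No procedure, sample size or analysis changes.

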9.2 Expedited reporting of SAEs

All SAEs, regardless of causality, must be reported to RM-CTU within 24 hours of knowledge of the event. SAEs should be documented on an SAE report form.

This form should be sent to:

Email: [contact]

[contact]

Each episode of an SAE must be recorded on a separate SAE report form. The NCI CTCAE v4.03 (Appendix 4) must be used to grade each SAE, and the worst grade recorded. If new or amended information on a previously reported SAE becomes available, the Investigator should report this to the RM-CTU on a new SAE report form. If the SAE has not been reported within the specified timeframes, a reason for lateness must be included when sending the SAE report form. Should the Investigator become aware of any drug-related SAEs after the patient goes 'off study', these must also be reported within the specified timelines above.

9.2.1 Events exempt from being reported as SAEs

Events specified in this section do not require reporting as SAEs in this trial, unless hospitalisation is prolonged for any reason and then an SAE form must be completed. The events must still be recorded in the appropriate section of the case report form (eCRF).

Underlying disease - Any events considered related to the underlying disease, such as disease progression, do not require SAE reporting.

Elective admissions

Elective admissions to hospital for procedures which were planned and documented in the medical records at the time of consent are not SAEs, and do not require SAE reporting. Hospitalisation for administration of the IMP, or to facilitate study procedures such as pharmacokinetic sampling according to the trial protocol is also exempt from being reported as an SAE.

9.3 Recording of AEs and SAEs in eCRFs

All AEs, including SAEs, must be recorded in the eCRF for eligible patients. All concomitant medications, including herbal medications and supplements must be recorded. Any therapy used to treat the event must be recorded. The eCRF will be reconciled with the safety database during and at the end of the trial. Therefore, the sites should ensure the data entered on the SAE report form and the data entered into the eCRF are consistent. The SRC and the Investigator(s) will regularly review the safety data.

9.4 Follow-up of AEs

Follow-up will continue until all the necessary safety data for the event has been gathered and until the drug-related AE or SAE has either resolved, returned to baseline or stabilised, or the patient has received further anti-cancer therapy. Requested follow-up information should be reported to the RM-CTU in a timely manner and as soon as possible after receipt of the follow-up request. For fatal or life-threatening cases, follow-up information should be reported as soon as possible.

9.5 Urgent safety measures

The Sponsor or Investigator may take appropriate urgent safety measures (USMs) in order to protect the patient of a clinical trial against any immediate hazards to their health or safety.

USMs may be taken without prior authorisation from the competent authority.

The Medicines and Healthcare products Regulations Agency (MHRA) and the Research Ethics Committee (REC) must be notified immediately and in any event within 3 days. Both parties will be notified by telephone immediately and in writing within 3 days of such measures being taken.

Should the site initiate a USM, the Investigator must inform the Sponsor immediately either by:

Email: [contact]
[contact]
[contact]

The notification must include:

- The date of the USM;
- Who took the decision; and
- Why the action was taken.

The Sponsor will then notify the MHRA and main REC within 3 days of the USM initiation. The Sponsor will distribute the response and any subsequent amendments to the trial sites.

CI Contact Details:

Name: [name]
Address: Renal and Melanoma Unit
The Royal Marsden NHS Foundation Trust
[name]
[contact]
[contact]

9.6 Pregnancy

The Investigator must make every effort to try and ensure that a clinical trial patient or their partner does not become pregnant during the trial or for 6 months afterwards. This should

be done and documented as part of the consent process by explaining clearly to the patient the potential dangers of becoming pregnant and also providing each patient with information about appropriate medically approved contraception. Two forms of medically approved contraception should be used, such as:

- Oral contraceptive and condom
- Intra-uterine device and condom
- Diaphragms with spermicidal gel and condom

Contraceptives should be used for 4 weeks before the patient joins the trial, throughout the trial and for 6 months after completing the trial.

It should be explained to male patients that if his partner is able to become pregnant, is pregnant or breast feeding when he enters the trial, he should use barrier methods of contraception (condom plus spermicidal gel) to prevent exposure to the IMP. However, if a patient or a partner of a patient does become pregnant the reporting procedures below must be followed:

Any pregnancy occurring in a patient or a patient's partner during treatment or within 6 months of the last IMP administration must be reported within 24 h of the site staff becoming aware of it using a Pregnancy Notification Form. It is the Investigator's responsibility to obtain consent for follow-up from the patient or patient's partner. The pregnancy outcome must be reported to RM-CTU, using a Pregnancy Outcome Form.

The Investigator must ensure that all patients are aware at the start of a clinical trial of the importance of reporting all pregnancies (in themselves and their partners) that occur whilst being treated with the IMP and occurring up to 6 months after the last IMP administration. The Investigator should offer counselling to the patient and/or the partner, and discuss the risks of continuing with the pregnancy and the possible effects on the foetus. Monitoring of the patient and the baby should continue until the conclusion of the pregnancy, if the patient or patient's partner has consented to this.

9.6.1 Other definitions of outcome

Toxic death: Any death to which drug toxicity is thought to have a major contribution.

Early death: Death during the first 28 days of treatment.

10 DATA ANALYSIS AND STATISTICAL CONSIDERATION

10.1 General considerations

This is an open-label, dose-escalating, non-randomised, multi-centre Phase 1 study of continuous once daily oral administration of CCT3833 as a single agent. The study will proceed in two separate parts. In Part A, dose escalation will proceed to establish MTD, pharmacokinetic data and relate this to pharmacodynamics data from tumour tissues, using a rolling six design. In Part B, the population will be enriched for melanoma patients, with BRAF or RAS mutations. Patients enrolled in Parts A and B will continue until toxicity, disease progression, or the meeting of an alternative withdrawal criterion.

10.2 Sample size

The sample size for this Phase 1 trial is not based on a formal sample size calculation as no formal statistical hypothesis is being tested. The total number of patients has been based on the desire to obtain adequate tolerability, safety, pharmacokinetic and pharmacodynamics data while exposing as few patients as possible to the IMP and procedures. The total number of patients required will depend upon the toxicities encountered and the number of dose cohorts required.

In Part A, the minimum number of patients will be 3, if there are 2 DLTs at the starting dose. The maximum number of patients is expected to be 42.

In Part B, there are 3 different patient cohorts each including 9 recruited patients, leading to a maximum of 27 patients within the expansion phase. An additional small number of patients from Part A may continue on treatment into Part B if they meet the inclusion criteria. These patients will be in addition to the 27 new patients recruited to Part B.

10.3 Statistical analysis

All quantitative data will be presented as number of observations, mean, standard deviation, minimum and maximum values. Qualitative data will be presented as number of observations and percentages. When appropriate, data will be presented together with 95% confidence intervals.

Baseline characteristics will be summarised for all enrolled patients. Patients who died or withdrew before treatment started or did not complete the required safety observations will be described and evaluated separately. Treatment administration will be described for all cycles. Dose administration, dose modifications or delays and the duration of therapy will be described.

The trial aims to determine the following endpoints:

Primary:

- a. Establishing the MTD and RP2D of CCT3833 (Part A only)
- b. Assess the safety and tolerability profile of CCT3833 (Part A and B)

Secondary:

- a. Establish pharmacokinetic parameters using the plasma levels of CCT3833 (Part A only)
- b. Measure response using radiological/clinical criteria (Part A and B)
- c. Determine the correlation between pharmacokinetic parameters and tolerability (Part A only)

Exploratory:

- a. Measurement of pharmacodynamics biomarkers (Parts A and B)
- b. Determine the magnitude and duration of effect of PD biomarkers (Parts A and B)

10.3.1 Safety and toxicity:

Safety data will be collected from the date of written consent. Safety variables will be summarised by descriptive statistics. The number and percentage of patients experiencing DLT or non-DLT toxicity in each dose level will be tabulated and the number of cohorts recruited in Part A will be recorded, respectively. AEs will be coded using MedDRA and reported for each dose level and presented as tables of frequency of AEs by body system and by worst severity grade observed. Tables should indicate related and unrelated events. The number and percentage of toxicity grades 1-4 and grade 3-4 respectively, experienced by those patients recruited in Part B will be reported. Laboratory data will be presented by dose level at each observation time. Values outside normal limits will be identified and summarised by frequency distribution.

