5.5 Patient evaluability

All patients who meet the eligibility criteria and receive at least one administration of CCT3833 will be evaluable for safety.

Patients who receive less than 75% of the planned doses of CCT3833 during the first treatment cycle (for reasons other than toxicity) will not be evaluable for dose review decisions. Patients who are not evaluable may be replaced.

All patients who meet the eligibility criteria, receive at least 75% of the planned doses of CCT3833 in the first treatment cycle, and have a baseline assessment of disease will be evaluable for disease response according to the RECIST criteria v1.1 (Appendix 5). To be assigned a status of complete response (CR) or partial response (PR), changes in tumour measurement must be confirmed by repeat measurements performed no less than 4 weeks after the response criteria are met. To be assigned a status of stable disease (SD), follow-up measurements must have met the SD criteria at least once, and at least 6 weeks after the first dose of CCT3833 has been taken.

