6.12 Discontinuation/withdrawal of participants from trial treatment

Each participant has the right to withdraw from the trial at any time. In addition, the Investigator may discontinue a participant from the trial at any time if the Investigator considers it necessary for any reason including:

- Pregnancy.
- Ineligibility (either arising during the trial or retrospectively, having been overlooked at Screening).
- Serious deviation of the study protocol (including persistent patient attendance failure and persistent non-compliance).
- An AE (or SAE), which requires discontinuation of the trial medication or results in inability to comply with trial procedures.
- Withdrawal of consent.
- Evidence of disease progression.
- Withdrawal by the Investigator.
- Sponsor's decision to terminate the study.

All results of the evaluations and observations to the point of withdrawal, together with a description of the reasons for withdrawal from the study, must be recorded in the medical records and in the eCRF. Patients who are removed from the study due to AEs (clinical or laboratory) will be treated and followed according to accepted medical practice. All pertinent information concerning the outcome of such treatment must be recorded in the eCRF and on the SAE report form where necessary.

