8.2.3 Off-study evaluations

These must be performed 28 days (± 3days) after the last dose of CCT3833, and should include the following at a minimum:

- Assessment of AEs and concurrent medications.
- ECOG Performance status.

- Physical examination and weight.
- Vital signs.
- Blood tests (including for tumour markers).
- ECG.
- Radiological/Clinical disease assessment.
- Subsequent tumour biopsy – optional.

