10.4 Timing of analyses

Toxicity data will be reviewed by the SRC prior to any decision regarding dose escalation or opening of new dose cohorts.

The final analysis will be conducted after one of the following conditions is met:

- The study is terminated early (for example, due to toxicity).
- All patients have had the opportunity to receive 12 cycles of treatment and are either continuing with treatment or have completed their 'Off-study' visit (i.e. 14 days (± 7 days) after the last dose of CCT3833).
- N.B. All patients are allowed to continue with CCT3833 treatment beyond 12 cycles if they are receiving therapeutic benefit.

Once one of the conditions is met, a data cut-off date will be established. All patient visits occurring on or before this date will be analysed and summarised in the final clinical study report. Any data collected after this date will be summarised in a supplemental report.

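### The primary safety analysis does not fix which dosed patients, which grades and how much follow-up it counts, so reported toxicity can be misstated

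*Combined protocol and SAP*

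**What the plan says.** Section 10.3 lists the safety and tolerability profile as a primary endpoint for Parts A and B. Four places govern how it is analysed.

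- **Safety set.** Section 5.5: "All patients who meet the eligibility criteria and receive at least one administration of CCT3833 will be evaluable for safety". Section 6.12 lists among the reasons for discontinuing a participant: "Ineligibility (either arising during the trial or retrospectively, having been overlooked at Screening". Section 9.3 adds: "All AEs, including SAEs, must be recorded in the eCRF for eligible patients". Section 9.1.2 also states its adverse-event (AE) collection period for eligible patients.
- **Incomplete observation.** Section 10.3, between the sentences on baseline characteristics and treatment administration: "Patients who died or withdrew before treatment started or did not complete the required safety observations will be described and evaluated separately". The required observations are not defined.
- **Grades in Part B.** Section 10.3.1: "The number and percentage of toxicity grades 1-4 and grade 3-4 respectively, experienced by those patients recruited in Part B will be reported". The same paragraph also plans AE tables by dose level, body system and worst grade, with no upper grade limit. Section 9.6.1 defines toxic death and early death, but 10.3 assigns neither to a table.
- **Follow-up at the final analysis.** Section 10.4 glosses the Off-study visit as "i.e. 14 days (± 7 days) after the last dose of CCT3833". Section 8.2.3 says of that visit: "These must be performed 28 days (± 3days) after the last dose of CCT3833", and 8.1.3 gives the same timing for Part A. Under 9.1.2, AE collection "continues for 28 days after the last administration of the IMP". Section 10.4 sends data collected after the cut-off to a supplemental report.

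**The concern.** A safety analysis should count everyone exposed, every grade including fatal events, and the whole planned observation window. Each of these is left open here.

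Eligibility does not change whether the drug harmed someone who took it, so a dosed patient later found ineligible belongs in the set. A dosed patient whose observation is incomplete may be incomplete because of toxicity or death, in which case membership of the main tables depends on the outcome being measured. A Part B summary that stops at grade 4 does not count the worst outcome. A final analysis triggered on a 14-day visit can precede the end of the 28-day AE window.

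The numbers are small: 3 to 6 patients per dose level in Part A and 9 per cohort in Part B. One patient therefore changes a reported percentage visibly. Section 2.1 says Part B is meant to support the design of later trials, so these percentages will be used.

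**Working it through.** **The plan's own figures.** Part B: 3 cohorts × 9 = 27 (10.2). Total: 42 + 27 = 69 (2.1). Both reproduce. Section 10.2 states that no hypothesis is tested, so no power calculation applies. The documents give no toxicity rates, so the event counts and rates below are illustrative assumptions. Intervals are exact (Clopper-Pearson) 95%.

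**Step 1: setting one dosed patient aside (5.5 eligibility condition, or the 10.3 sentence).** The patient leaves numerator and denominator together.

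- Cohort of 9, two patients with a grade 3 or higher event: 2/9 = 22.2% (2.8 to 60.0).
  - Omitted patient had an event: 1/8 = 12.5% (0.3 to 52.7).
  - Omitted patient had none: 2/8 = 25.0% (3.2 to 65.1).
- All 27 Part B patients, three with an event: 3/27 = 11.1% (2.4 to 29.2).
  - Omitted patient had an event: 2/26 = 7.7% (0.9 to 25.1).
  - Omitted patient had none: 3/26 = 11.5% (2.4 to 30.2).

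In general, with a fraction f set aside, rate r0 in those kept and r1 in those set aside, the all-dosed rate is (1 − f) × r0 + f × r1. With f = 10% and r0 = 20%:

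- r1 = 50%: 0.9 × 20% + 0.1 × 50% = 23%
- r1 = 20%: 0.9 × 20% + 0.1 × 20% = 20%
- r1 = 0%: 0.9 × 20% + 0.1 × 0% = 18%

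The reported 20% is too low only if the set-aside patients have more toxicity than those kept.

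**Step 2: Grade 5 outside the Part B summary.** The denominator stays, so the count can only fall. If one of the patients with a grade 3 or higher event had a fatal one that is not counted:

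- 3/27 = 11.1% becomes 2/27 = 7.4%.
- In one cohort, 2/9 = 22.2% becomes 1/9 = 11.1%.

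The chance that at least one of 27 patients has a Grade 5 event is 1 − (1 − p)^27. For assumed p of 1%, 2%, 5% and 10% this is 23.8%, 42.0%, 75.0% and 94.2%.

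**Step 3: the two visit timings.**

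- Section 10.4: 14 ± 7 gives day 7 to day 21 after the last dose.
- Sections 8.1.3 and 8.2.3: 28 ± 3 gives day 25 to day 31.
- Section 9.1.2: AE collection to day 28.

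The first two ranges do not overlap. Days of the AE window still open at the 10.4 visit: 28 − 21 = 7 (25%), 28 − 14 = 14 (50%), 28 − 7 = 21 (75%). Even a visit at day 25 leaves 28 − 25 = 3 days open. This matters only for patients whose last dose falls shortly before the cut-off.

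**Step 4: dose decisions.** Sections 5.5 and 6.6 make under-dosed Cycle 1 patients non-evaluable for dose review only when the reason is not toxicity. Section 6.5 uses a count of DLTs, not a percentage. None of the four rules enters that count.

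**The case against.** The other side has good arguments on each item.

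- **Incomplete observation.** Section 5.5 has no completeness condition, so an eligible dosed patient who dies or stops early is evaluable for safety. The 10.3 sentence stands outside 10.3.1 and promises separate description, not removal from the AE tables. This stands as a possible reading. But the clause on incomplete observation is not clearly limited to never-dosed patients, and nothing says that dosed patients also stay in the main tables.
- **Ineligible patients.** Section 6.12 requires results up to withdrawal to be recorded in the eCRF, 9.2 requires all SAEs to be reported, and the eligible-patient wording may simply contrast with screening failures. This answers much of the recording question. It does not answer the eligibility condition in 5.5, nor non-serious AEs after such a patient is withdrawn.
- **Grade 5.** A reader might infer that fatal events are omitted from the Part B analysis altogether. The documents do not support that. The worst-grade tables have no cap, so a fatal AE may appear there, and 6.7.2 has the Safety Review Committee meet within a week of any death. The gap is in the one summary specific to Part B.
- **Visit timing.** The 14-day text is a parenthetical gloss, the cut-off date is set only after the trigger is met, AE collection stays at 28 days, and later data are reported in a supplement. All true. The contradiction remains, and the final report could still be incomplete for the last patients.

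A reader might also infer that the primary safety endpoint is biased low by construction, or that the MTD is affected. Step 1 shows that the exclusions can move a rate either way, and step 4 shows that dose decisions keep toxicity-related under-dosing.

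**Conclusion.** The point holds as a defect in how a primary endpoint is specified, not as a demonstrated bias.

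- The eligibility condition in 5.5 can remove exposed patients; the direction of the effect is not established.
- The 10.3 sentence, on one reading, conflicts with the one-dose rule in 5.5. It could bias toxicity downward if toxicity or death causes the incompleteness. That cause is plausible, but it is an assumption.
- The Part B summary, taken literally, does not count a fatal toxicity. Here alone the direction is certain, and it is confined to that summary: 3.7 percentage points per event in 27 patients (1/27) and 11.1 per event in a cohort of 9 (1/9).
- The 14-day and 28-day timings contradict each other. The final report could miss 7 to 21 AE days for patients stopping just before the cut-off, with those data going only to the supplemental report.

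The rates and counts are illustrative; the conflicts between sections do not depend on them. The analysis set and grade range should be settled before the data are seen.

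**What to change.** 1. In 5.5 and 10.3, define the safety set as every patient who received at least one dose of CCT3833, the run-in dose included, regardless of eligibility or completeness of observation. Describe separately only patients who were never dosed.
2. Align the eligible-patient wording in 9.3 and 9.1.2 so that AEs of all dosed patients are recorded.
3. In 10.3.1, report Part B as grades 1-5 and grades 3-5, and add the toxic and early deaths defined in 9.6.1.
4. Reconcile 10.4 with 8.1.3, 8.2.3 and 9.1.2, and set the data cut-off so that the final analysis covers the full AE collection window for every patient off treatment.

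The cost is mainly wording. It also means AE capture for the few dosed patients found ineligible, about two weeks at the data cut (28 − 14 = 14 days), and toxicity figures that may look slightly less favourable.
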